## 4.0 OVERVIEW OF STUDY DESIGN/INTERVENTION

### 4.1 Design

**Phase Ib:** The phase Ib portion of the study is designed to determine the MTD of romidepsin and lenalidomide. All patients must have a relapsed or refractory B-cell lymphoma, T-cell lymphoma, or multiple myeloma. Patients will be treated on a 28-day cycle with romidepsin infused on day 1, 8, and 15, and lenalidomide taken orally on days 1-21. The design is a standard 3+3 dose escalation (Table 1) of romidepsin and lenalidomide. The first cohort will enter at dose level 1.

Dose Level	Romidepsin	Lenalidomide
-1	8 mg/m 	10 mg
1	8 mg/m 	15 mg
2	8 mg/m 	25 mg
3	10 mg/m 	25 mg
4	14 mg/m 	25 mg

Table 1: Description of dose level

DLT is defined in cycle 1 (in phase Ib).

Definitions:

- Grade  $\geq$  3 non-hematologic (attributed to study drugs)
- Grade 4 hematologic toxicities (attributed to study drugs) defined as:
  - Grade 4 thrombocytopenia (platelets  $< 25$  K/ $\mu$ L)
  - Grade 4 neutropenia (absolute neutrophil count (ANC)  $< 0.5$ )
- Grade 3 thrombocytopenia or neutropenia that results in a  $> 3$  day delay in any romidepsin dose in cycle 1.
- One week or greater delay in initiating cycle 2 day 1 due to continued drug-related toxicity.

Any patient with an adverse event that meets the DLT definition is considered evaluable for MTD determination. Patients who do not have a DLT, but received  $<3$  doses of romidepsin or  $<80\%$  (17/21) of the doses of lenalidomide during cycle 1 will not be evaluable for MTD and will be replaced.

Three patients will be initially treated in each cohort until the MTD is determined. If dose level 4 (full dose of each drug) is achieved without DLT after 1 cycle that dose level will be deemed the optimal dose and the study will proceed to a phase IIa expansion cohort. Patients treated at MTD in the phase Ib portion will be counted towards the phase IIa accrual by disease subtype and also for all efficacy and toxicity endpoints unless they did not have measurable disease at point of study entry as allowed in the phase Ib portion.

**Phase IIa:** The phase IIa portion will further assess the toxicity and safety and allow a preliminary assessment of the efficacy of the combination to provide background for a potential future subtype specific phase II study (see Section14.0).

DLT is defined in cycles 1-4 (in phase IIa)

Definitions:

- Grade  $\geq$  3 non-hematologic (attributed to study drugs)

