- Grade 4 hematologic toxicities (attributed to study drugs) defined as:
  - Grade 4 thrombocytopenia (platelets  $< 25$  K/ $\mu$ L)
  - Grade 4 neutropenia (absolute neutrophil count (ANC)  $< 0.5$ )
- Grade 3 thrombocytopenia or neutropenia that results in a  $> 4$  day delay in any romidepsin dose in cycle 1.
- One week or greater delay in initiating cycle 2 day 1 due to continued drug-related toxicity.

At the time of enrollment the patients will be identified as representing three cohorts based upon disease subtype: 1) B-cell lymphoma 2) multiple myeloma 3) PTCL. Each disease specific cohort will enroll 15 patients. We plan to accrue 38 patients into the phase IIa portion including those treated at the MTD of the phase Ib portion. The assessment of toxicity and efficacy will be performed within the entire cohort evaluable at MTD. A preplanned exploratory analysis of the toxicity and efficacy of the disease specific cohorts will also be performed. Efficacy measures which will be determined include ORR, CBr (for myeloma), TTR, DOR, and EFS. ORR is defined as the percentage of patients achieving a best response of CR/CRu, very good partial response (VGPR--myeloma only), or PR at any disease assessment time point. CBr is defined as CR, VGPR, PR or MR (minimal response) in myeloma patients. TTR is defined as the time or number of cycles between study registration and documentation of first response (CR/Cru, VGPR, or PR). DOR is defined as the time or number of cycles between documentation of first response and progression, change of therapy, death, or date of last contact (if still alive without progression). EFS is defined as the time between study registration and documented progression, change in therapy, or death if no progression was observed.

[figure not shown]

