**\*1 cycle equals 28 days**

### **9.3 Treatment Plan romidepsin/lenalidomide Phase IIa**

The entire accrual is planned to have up to 51 patients in the phase IIa portion; each disease cohort will have 15 patients (B-cell lymphoma, multiple myeloma or PTCL). There will be an expansion of the T-cell cohort to include an additional 6 patients with acute T-cell leukemia/lymphoma. After a sufficient number of patients have been enrolled for determination of the primary and secondary objectives, cohorts may be closed to accrual by the MSK principal investigator. The MTD for lymphoma has been determined to be 14mg/m^2 romidepsin on Days 1, 8, 15 and 25mg lenalidomide from Days 1-21. The patients treated at MTD in the phase Ib cohort (if measurable disease at enrollment) and phase IIa cohort will be evaluated both collectively and by disease subtype. Patients with more than one histology are eligible and will be assigned by the principal investigator to a specific disease subtype.

- In patients with MM, due to the presence of toxicities, patients will be dosed at romidepsin 10mg/m^2 and lenalidomide 25mg (see table 2a). If two of six (or fewer) patients treated at this dose level develop dose-limiting toxicities, the initial dosing for subsequent patients will be decreased to romidepsin

10mg/m^2 and lenalidomide 15mg. For example, if two of four patients treated at this initial dose develop dose-limiting toxicities, the starting dose for subsequent patients will be reduced as above.

- At a starting dose of romidepsin 10mg/m^2 and lenalidomide 15mg, should 2 of 6 (or less) patient will be reduced to romidepsin 8mg/m^2 and lenalidomide 15mg.
- At a starting dose of romidepsin 8mg/m^2 and lenalidomide 15mg, should 2 of 6 (or less) patients have dose-limiting toxicities, the initial dose for subsequent patients will be reduced to romidepsin 8mg/m^2 and lenalidomide 10mg.

Table 2a: Multiple Myeloma Dosing for Phase IIa Portion

Dose level	Romidepsin	Lenalidomide
1	10	25
-1	10	15
-2	8	15
-3	8	10

The treatment plan for the phase IIa portion is described below:

Romidepsin/Lenalidomide Cycle 1 Day 1 + subsequent Cycle X

Romidepsin MTD IVPB over 4 hours

Lenalidomide MTD PO q days 1-21

Romidepsin/Lenalidomide Cycle 1 Day 8

Romidepsin MTD IVPB over 4 hours

Romidepsin/Lenalidomide Cycle 1 Day 15

Romidepsin MTD IVPB over 4 hours

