**Table 7: Study Evaluation Schedule**

Procedure	Screening	Cycle 1				Cycle 2 and beyond**				End of study
		Day 1	Day 8	Day 15	Day 22	Day 1	Day 8	Day 15	End of cycle	
Record prior medications, treatments	X									
Record prior anti-cancer therapies	X									
Physical examination 	X	X	X	X	X 	X				X
ECOG performance status 	X	X				X				X
12 Lead ECG 	X	X	X	X		X	X 	X		
Hematology	X	X	X	X		X	X 	X		X
LDH 	X					X				
Electrolytes 	X	X	X	X	X 	X	X 	X		X
Liver function analysis 	X	X				X				X
Pregnancy testing 	X	X	X	X	X 	X				X
REMS ® program (patient enrollment)	X									
Start lenalidomide 		X				X		X		
Romidepsin 		X	X	X		X	X 	X		
Disease/Response assessment 	X								X 	
Record adverse events 		X				X		X		X
Record concomitant medications		X				X		X		X

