**Table 7 Legend**

\* Romidepsin dosing may be delayed up to 3 days of the scheduled visit. Romidepsin doses must be given at least 7 days apart and all doses completed by day 21 of each cycle. In cycle 1, labs may be performed up to 1 day prior to treatment. After completion of cycle 1, labs may be performed up to 3 days prior to treatment.

\*\* For cycle 2 and beyond, study procedures should be performed per the study evaluation schedule ( $\pm 3$  days) while maintaining the minimum dosing spacing for romidepsin as above.

If Physical examination, vital signs, weight and ECOG performance status were done within 7 days of Day 1, they do not need to be repeated at study cycle X, Day 1 (excluding cycle 1 in the phase Ib portion). An unscheduled visit can occur at any time during the study.

The schedule for ECG monitoring is found in section 10.5 and romidepsin dose modifications in Table 6. After cycle 2 the schedule can be amended as clinically indicated in section 10.5.

Sodium, potassium, chloride, bicarbonate, BUN, creatinine, calcium, and glucose are part of the electrolyte assessment at every time point. **Magnesium** will be added to the electrolyte panel at **screening, days 1, 8 and 15 of the treatment cycle, and at the end of study visit**. **Liver function analysis** (at least total protein, albumin, AST,

ALT, alkaline phosphatase, total bilirubin) is necessary on day 1 of each cycle (within windows for labs provided depending on the cycle of treatment). The LDH may be omitted in patients with multiple myeloma.

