## 14.0 BIOSTATISTICS

The standard dose-escalation scheme for this study is as follows. Patients will be accrued to the study in cohorts of 3. For any given dose an initial cohort of 3 patients will be treated at that dose. The dose level will be escalated if none of the 3 patients exhibits any DLT in the first cycle as defined in section 4.1. If a DLT is observed in one patient, an additional cohort of 3 patients will be treated at that dose. The dose will be escalated if none of the additional 3 patients exhibits any DLT. Dose-escalation stops and the previous dose will be considered the MTD if 2 or more patients have a DLT. If the previous dose level has been administered to only 3 patients, an additional 3 patients will be enrolled to confirm the result. For this design the probability of escalation is as follows:

True toxicity rate	5%	10%	15%	20%	25%	30%	40%	50%
Probability of escalation	0.97	0.91	0.81	0.71	0.60	0.49	0.31	0.17

Dose escalation will start with dose level 1. A dose level -1 is also added to the design to ensure a minimum level of toxicity (we expect this dose level will be quite tolerable for patients). The maximum number of patients needed for this dose escalation design is 30. Patients with measurable disease treated at MTD in the phase Ib will be analyzed in phase Ila to further characterize the toxicity of romidepsin and lenalidomide in combination at the MTD determined by phase Ib. In phase Ila, we plan to enroll about 39 patients so that the total number of patients to be treated at MTD will be approximately 44 (we plan to enroll 15 patients with B-cell lymphomas, 8 patients with multiple myeloma, 15 patients with T-cell lymphomas and additional 6 patients with acute T-cell leukemia/lymphoma). To subsequently monitor the safety primary endpoint in the phase Ila portion, we will employ a dose-reduction plan for the predefined DLT in the phase Ib portion during cycles 1-4. This dose-reduction plan specifies that the dose will be reduced from the phase Ib MTD to the MTD-1 (10mg/m^2 romidepsin; 25mg lenalidomide) if DLT occur in cycle 1-4 in: ≥8/first 15; ≥16/first 30; or if more than 24 patients when the last (45th) evaluable patient has completed the trial have any DLT. If at MTD-1 a DLT occurs in ≥8/first 15; ≥16/first 30, then MTD-2 (8mg/m^2 romidepsin; 25mg lenalidomide) will be employed for the remainder of phase Ila. The probability of dose-reducing from the MTD is the following:

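### A grade 4 cytopenia of any duration is a DLT, yet no blood count is scheduled between day 15 and cycle 2 day 1, so brief silent nadirs go uncounted

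*Combined protocol and SAP*

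**What the plan says.** Section 4.1 lists "Grade 4 hematologic toxicities (attributed to study drugs) defined as" platelets below 25 K/µL or ANC below 0.5. It sets no minimum duration. The window is cycle 1 in phase Ib and cycles 1-4 in phase IIa. Section 4.1 also makes a delay of a week or more in starting cycle 2, from continuing drug toxicity, a DLT.

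Section 14 applies this to the phase IIa dose: "we will employ a dose-reduction plan for the predefined DLT in the phase Ib portion during cycles 1-4". The dose drops at 8 or more DLTs in the first 15 patients, 16 or more in the first 30, or more than 24 of 45. Section 9.3 has a separate myeloma rule: two DLTs in six or fewer patients lower the starting dose for later patients.

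Table 7 marks hematology on days 1, 8 and 15. The cycle 1 day 22 column (with a window of 3 days either way) has physical examination, electrolytes and pregnancy testing, but its hematology cell is empty. From cycle 2 on there is no day 22 column.

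The Table 7 legend allows some movement: "Romidepsin dosing may be delayed up to 3 days of the scheduled visit", "After completion of cycle 1, labs may be performed up to 3 days prior to treatment", and "An unscheduled visit can occur at any time during the study".

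Section 17.4 words the DLT differently. Grade 4 thrombocytopenia counts at any duration, but neutropenia counts only if the ANC has not recovered within 14 days of last treatment. Its cycle 2 item is an inability to receive day 1, with no one-week threshold.

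**The concern.** The definition counts a grade 4 value even if it lasts a day, while the schedule leaves a two-week interval in which no such value can be seen by a planned test. That interval follows the third romidepsin dose and includes the last week of lenalidomide, which runs to day 21. A missing count can hide a DLT but cannot create one.

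Two things are at stake. First, DLT counts drive the phase IIa rule and the myeloma step-down, and they are the reported primary safety result. Second, Table 5 holds both drugs for grade 3 or worse thrombocytopenia, and section 9.9.2 holds prophylactic anticoagulation below 50,000 platelets. In that interval no scheduled count can trigger either hold.

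**Working it through.** **Length of the interval.** Nominally day 15 to day 29, which is 14 days. At the shortest, a day 15 dose given 3 days late (day 18) and labs drawn 3 days early (day 26) leave 26 - 18 = 8 days.

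**What else could catch the episode.**
- Table 5 asks for a weekly CBC only after a grade 3 or worse cytopenia has been found.
- Section 10.2 checks counts only before romidepsin doses.
- Section 10.1 needs ANC at least 1.0 and platelets at least 70 K/µL (or within 10 K of baseline) to start a cycle, otherwise weekly re-evaluation. With weekly rechecks, a drug-related cytopenia still below those limits on day 29 normally becomes a one-week delay, and so a DLT.
- Unscheduled visits may catch symptomatic cases.

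What is lost is a silent episode that starts after day 15, reaches grade 4, and is back at the start limits by day 29 (or at a recheck less than a week later).

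**The plan's own figure.** An exact sequential binomial with boundaries 8/15, 16/30 and at least 25/45 gives 0.241 at a 40% DLT rate; section 14 prints 0.243. Of this, 0.213 arises at the first 15 patients. (At 50% it gives 0.607 against a printed 0.632; a boundary of 24 or more gives 0.630.)

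**Assumptions, none of them in the documents.** Onset is uniform over the 14 days. Grade 4 lasts L = 3, 5 or 7 days. A further R days pass between the end of grade 4 and the start limits. A quarter to a half of grade 4 episodes fall in this interval. For the grade 4 rate I use 8.2%, 16% and 33%, which sections 3.2.3.2 and 3.2.3.3 quote for lenalidomide alone over whole studies.

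**Share of gap episodes that a day 22 count adds.** Without it, the share missed is (14 - L - R)/14. With it, the share missed is [max(0, 7 - L) + max(0, 7 - L - R)]/14. The difference is min(L, 7 - R)/14 for R up to 7:

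| R (days) | L = 3 | L = 5 | L = 7 |
|---|---|---|---|
| 0 | 0.214 | 0.357 | 0.500 |
| 2 | 0.214 | 0.357 | 0.357 |
| 4 | 0.214 | 0.214 | 0.214 |
| 7 | 0 | 0 | 0 |

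**Percentage points of patients, h = grade 4 rate × share in gap × share added.**
- Low, R up to 4: 8.2% × 0.25 × 0.214 = 0.44.
- Middle, R up to 2: 16% × 0.5 × 0.357 = 2.9.
- High with R = 4: 33% × 0.5 × 0.214 = 3.5.
- High with R = 0: 33% × 0.5 × 0.500 = 8.25.

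**Effect on the rules.** Some of these patients have another detected DLT. With independence, a rate p seen with the day 22 count becomes 1 - (1 - p)/(1 - h) without it.

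| h (points) | p = 40% becomes | Phase IIa reduction (0.241) becomes | p = 30% becomes | Myeloma, at least 2 of 6 (0.580), becomes |
|---|---|---|---|---|
| 0.44 | 39.7% | 0.234 | 29.7% | 0.573 |
| 3.0 | 38.1% | 0.191 | 27.8% | 0.532 |
| 3.5 | 37.8% | 0.182 | 27.4% | 0.523 |
| 8.25 | 34.6% | 0.115 | 23.7% | 0.435 |

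The phase IIa column is an upper figure, because a patient missed in cycle 1 may be caught in cycles 2-4.

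**Late start.** If the count begins at patient 16, the first 15 patients run at the lower rate and the next 30 at 40%. The probability moves from 0.191 to 0.198 (3 points), 0.182 to 0.191 (3.5 points), or 0.115 to 0.130 (8.25 points).

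**Cycle 1 only.** Suppose 40% have a DLT that is seen and a further 3% per cycle have one hidden in the gap. Full capture over four cycles gives 1 - 0.60 × 0.97^4 = 46.9%. Capture in cycle 1 alone gives 1 - 0.60 × 0.97 = 41.8%. The share recovered is 1.8/6.9, about a quarter.

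**The case against.** The strongest reply is that the plan already has a safeguard. The section 10.1 start limits and the one-week-delay DLT catch any cytopenia slow to recover, and patients held at day 15 already get weekly counts. This stands, and it rules out the largest figures. The 8.25-point case needs R = 0. But when grade 4 ends, the ANC is only at 0.5 against a start limit of 1.0, and platelets are only at 25 K/µL against 70 K/µL (or 10 K below baseline), so some days must pass. A recheck sooner than a week would weaken the safeguard, so it narrows the gap without closing it.

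The inputs can also be called generous: single-agent rates over whole studies, with up to half of the episodes placed in one fortnight. That stands too.

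Third, a late change does little for the pooled rule, and the documents do not say how many patients remain, or whether any of the 8 myeloma patients planned in section 14 do. This limits the benefit to the dose rules. It does not touch the safety reason or the accuracy of the reported DLT rate.

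A reader might infer that the lymphoma MTD is wrong. The documents do not support this. Section 9.3 says "The MTD for lymphoma has been determined to be" 14 mg/m² romidepsin with 25 mg lenalidomide, and nothing shows that a missed nadir affected it. A reader might also infer that the phase IIa rule is about halved in sensitivity (0.241 to 0.115). That rests on the R = 0 extreme.

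**Conclusion.** The mismatch is real and follows from the text alone: a DLT of any duration, and a two-week interval with no scheduled count at a time when blood is drawn anyway. The direction is certain: DLTs can only be undercounted.

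The size is not derivable. Under the assumptions above it lies between near zero and a few percentage points of patients. With 4 days from the end of grade 4 to the start limits, the top is about 3.5 points; with 7 days, a day 22 count adds nothing. The myeloma rule is the more sensitive to single missed events, since two in six decide it, but whether it is still in use is not stated.

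A cycle 1 day 22 count should be added for safety and for more complete cycle 1 DLT counting. It should not be presented as repairing the phase IIa rule, since it covers one of four DLT cycles.

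The section 17.4 conflict is a separate but related fault. A grade 4 neutropenia that has recovered by day 29 is a DLT under 4.1 and not under 17.4, so sites could report the same event differently.

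**What to change.** - In Table 7, mark hematology in the existing cycle 1 day 22 column, with its 3-day window, for all remaining patients.
- In sections 9.3 and 14, state that a patient without a day 22 count stays in the denominator (the first 15, 30 or 45, or the myeloma six) and is classified on the counts available. Report how many such patients there are.
- Keep 8/15, 16/30 and more than 24/45 unchanged.
- Make section 17.4 refer to the section 4.1 DLT list, because its neutrophil and cycle 2 items differ.
- In the report, state that earlier patients, including those in phase Ib, had scheduled counts on days 1, 8, 15 and cycle 2 day 1 only.

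The cost is one extra tube per remaining patient at an existing draw, and a protocol amendment with IRB approval at MSK and the participating sites. No visits or patients are added. Later patients will be observed slightly more closely than earlier ones in the same rule; on the figures above this moves the pooled rule by at most about 0.015 at a 40% rate if it starts at patient 16. Nominal day 22 is also the day after the last lenalidomide dose, so a same-cycle drug hold gains only if the draw falls early in the window. The anticoagulation hold gains either way. Cycles 2-4 remain uncovered unless optional local counts are added.

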True toxicity rate	5%	10%	15%	20%	25%	30%	35%	40%	50%
Dose reduction prob.	0.000	0.000	0.001	0.004	0.016	0.056	0.118	0.243	0.632

18 months after the final patient is enrolled and after 80% of patients, MSKCC will analyze disease status, serious adverse events and survival for all patients.

Secondary objectives of this study aim at examining many clinical endpoints (see Sections 4 and 12 for detailed definitions). Overall response rate (ORR) and clinical benefit rate (CBr) for MM patients, complete response rate, very good partial response/partial response rate will be summarized using proportions and confidence intervals will be provided. Time to response, duration of response and event free survival will be analyzed by routine survival analysis tools such as Kaplan-Meier estimation or competing risks method. In this portion of the study, all three disease subtypes (B-cell lymphoma, multiple myeloma, PTCL) will be grouped together including those from the phase Ib that were treated at MTD. Note that the response criteria are different among the disease subtypes (see Section 12.0). To preliminarily collect the data, subset analyses will also be conducted to evaluate the ORR, TTR, DOR, and EFS for each disease subtype.

To further investigate activity of this regimen in patients with acute T-cell leukemia/lymphoma, an additional cohort of 6 patients will be added to the phase IIa portion of the study. When the true response rate is 30% or above, the probability that none of the 6 patients will respond is less than 0.12. Subset analyses will be conducted to evaluate the ORR, TRR, DOR, and EFS for each disease subtype.

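### Phase IIa dose-reduction table: the 50% DLT cell reads 0.632, but the rule as worded gives exactly 0.607

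*Combined protocol and SAP*

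**What the plan says.** Section 14.0 (Biostatistics) sets a dose-reduction plan for phase IIa, based on DLTs in cycles 1-4. The dose falls from the MTD to the next level down if DLTs occur in "≥8/first 15; ≥16/first 30; or if more than 24 patients when the last" (45th) "evaluable patient has completed the trial have any DLT". Taken literally, the third condition is met at 25 or more patients.

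The section then states: "The probability of dose-reducing from the MTD is the following". The row labelled "Dose reduction prob" reads:

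| True DLT rate | 5% | 10% | 15% | 20% | 25% | 30% | 35% | 40% | 50% |
|---|---|---|---|---|---|---|---|---|---|
| Printed | 0.000 | 0.000 | 0.001 | 0.004 | 0.016 | 0.056 | 0.118 | 0.243 | 0.632 |

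The section does not say whether these values are exact or simulated, and gives no number of runs.

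**The concern.** This row is the only stated operating characteristic of the rule that monitors the primary safety endpoint in phase IIa. It is printed to three decimals, so a reader will take it as accurate to about 0.001. The rule is three binomial looks and can be computed exactly. For the wording "or if more than 24 patients when the last", the cell at the highest toxicity rate does not agree with the exact value.

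Two things are at stake. The chance of acting at a 50% DLT rate may be slightly overstated. The text and the table may also use different final thresholds, in which case it is unclear whether exactly 24 patients with DLTs among 45 triggers the rule.

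**Working it through.** **Inputs, all from Section 14.0.** Looks after 15, 30 and 45 patients; thresholds of at least 8, at least 16, and more than 24 (at least 25); the nine true rates and printed probabilities above.

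**Formula.** Let X1, X2 and X3 be the numbers of patients with a DLT in successive groups of 15, each independent Binomial(15, p). The probability of acting is the sum of three terms:

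- Look 1: P(X1 ≥ 8)
- Look 2: P(X1 ≤ 7 and X1 + X2 ≥ 16)
- Look 3: P(X1 ≤ 7, X1 + X2 ≤ 15 and X1 + X2 + X3 ≥ 25)

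**The 50% cell.** The three terms are 0.5000, 0.0889 and 0.0178, which sum to 0.6067. The printed value is 0.632, and 0.632 − 0.6067 = 0.0253, or 2.5 points.

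**The whole row, under both readings of the last threshold.**

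| True DLT rate | Printed | Exact, ≥25 of 45 | Printed − exact (points) | Exact, ≥24 of 45 | Printed − exact (points) |
|---|---|---|---|---|---|
| 5% | 0.000 | 0.0000 | 0.00 | 0.0000 | 0.00 |
| 10% | 0.000 | 0.0000 | 0.00 | 0.0000 | 0.00 |
| 15% | 0.001 | 0.0006 | +0.04 | 0.0006 | +0.04 |
| 20% | 0.004 | 0.0043 | −0.03 | 0.0043 | −0.03 |
| 25% | 0.016 | 0.0176 | −0.16 | 0.0176 | −0.16 |
| 30% | 0.056 | 0.0520 | +0.40 | 0.0521 | +0.39 |
| 35% | 0.118 | 0.1222 | −0.42 | 0.1234 | −0.54 |
| 40% | 0.243 | 0.2412 | +0.18 | 0.2463 | −0.33 |
| 50% | 0.632 | 0.6067 | +2.53 | 0.6304 | +0.16 |

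With the wording as it stands, eight cells are within 0.42 points and one is not. With 24 or more, all nine are within 0.54 points. At 50% the third look then adds 0.0416 instead of 0.0178, while the first two looks still add 0.5889 together.

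**Final look at 44 instead of 45.** Section 14.0 also plans approximately 44 patients at the MTD. With the last look at 44 and a threshold of at least 25, the 50% value is 0.5985, further from print. This does not explain the gap.

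**Could it be simulation error?** The number of runs, N, is an assumption. The standard error of the 50% cell is √(0.6067 × 0.3933 / N). At N = 1,000 this is 0.0154, so z = 0.0253 / 0.0154 = 1.64. The joint chi-square sums z² over the seven non-zero cells (15% to 50%), on 7 df:

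| Assumed runs | z at 50%, ≥25 | Chi-square, ≥25 | p | Chi-square, ≥24 | p |
|---|---|---|---|---|---|
| 1,000 | 1.64 | 3.60 | 0.82 | 1.05 | 0.99 |
| 2,000 | 2.31 | 7.19 | 0.41 | 2.10 | 0.95 |
| 5,000 | 3.66 | 17.99 | 0.01 | 5.24 | 0.63 |

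The rule as worded is compatible with the row at 1,000 runs. At 2,000 the row as a whole still fits, though the 50% cell alone is strained. At 5,000 it does not fit. The reading of 24 or more fits better at every run count shown.

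**The case against.** The strongest reply is that Section 14.0 never calls the values exact. Small differences of both signs in the other cells (0.056 against 0.052, 0.118 against 0.122) look like simulation. If the row was simulated from the rule as worded with about 1,000 runs, a value of 0.632 is unremarkable: z = 1.64, before allowing for its being picked as the worst of seven non-zero cells. This stands. A reader might infer that the cell cannot have come from the printed rule, or that the text certainly contains an off-by-one error. The documents support neither, because they give no method and no run count. What simulation does not do is make 0.632 the correct value for that rule.

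The second reply is that almost nothing depends on it. The two readings of the threshold differ only at the third look, which the plan places after the 45th evaluable patient has completed. By then no accruing patient remains whose dose could be lowered. This also stands. A reader might infer that the discrepancy weakens patient protection during the trial, but the first two looks contribute 0.5889 at a 50% DLT rate under either reading.

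A reader might also link the gap to the "8 patients with multiple myeloma" in the planned total, because Section 9.3 starts myeloma patients at a lower romidepsin dose. That does not explain the gap. The table is set out for a single true toxicity rate and for reduction from the MTD, and the calculation here uses the same assumption.

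**Conclusion.** The point holds as a minor arithmetic discrepancy. For the rule as worded, the probability of dose reduction at a 50% DLT rate is 0.607, not 0.632, a difference of 2.5 points. The other eight cells are right to within 0.42 points. The calculation assumes independent DLTs at one common rate and looks at exactly 15, 30 and 45 patients.

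The cause is open. A final threshold of 24 or more reproduces the cell (0.630) and fits the row better jointly, but simulation from the printed rule at about 1,000 runs remains possible. At 0.61 or 0.63 the rule acts somewhat more often than not at a 50% DLT rate, so the description of the design hardly changes.

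**What to change.** Confirm the third threshold in Section 14.0, then make the text and table agree.

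- **If more than 24 is intended:** keep the wording and replace 0.632 with 0.607. Preferably print the full exact row for 5% to 50%: 0.000, 0.000, 0.001, 0.004, 0.018, 0.052, 0.122, 0.241, 0.607.
- **If 24 or more was intended:** change the wording of the third condition and print 0.630. The exact row is 0.000, 0.000, 0.001, 0.004, 0.018, 0.052, 0.123, 0.246, 0.630.

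The cost is one confirmed threshold and either one cell or one table row. Sample size, the first two looks and the analyses do not change. If the wording stands, the only loss is a 50% figure 2.5 points less favourable.
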